- The length of time from aneurysm rupture to time of surgical intervention
- Time in between vasodilator applications
- Number of drug applications used
- Dose of drug applications
- Pre- and post-procedure intracranial pressure measurements (ICPs)
- Cardiovascular instability (SBP changes in mm Hg, requirement of intravenous [IV] pressors)
- New strokes on CT
- Modified Rankin Scale, NIHSS (before treatment, at discharge, and at 3 months after discharge)

Patients will have a 3-month follow-up clinic visit as per standard of care after discharge from the hospital.

5. SELECTION AND ENROLLMENT OF SUBJECTS

Inclusion Criteria: Only adult patients ≥ 18 years with ruptured aneurysms requiring surgery or endovascular therapy and who experience vasospasm post-operatively (3-21 days post-procedure) will be enrolled in this study.

Informed consent will be obtained either from the patient or the patient's legal representative. The institutional PI/Co-PI will determine the **eligibility of the patients** for the study on the basis of the following:

- Adult patient, age 18 80 years old, with ruptured aneurysm(s) who experience vasospasm postoperatively within 3-21 days.
- Symptomatic vasospasm (clinical or TCD)
- For centers that perform a routine day 7 angiogram post-aneurysm treatment 50% or more stenosis seen on diagnostic angiogram for asymptomatic patients.

Exclusion Criteria:

- Inability to obtain consent from patient or patient's family
- Pregnant women (confirmed by a positive pregnancy test)
- Hunt Hess (HH) grade 5
- Intra-arterial drug treatment in all 3 arterial territories

Study Centers:

The University of Texas Medical School at Houston University of Illinois College of Medicine – Chicago Geisinger Health System, North Shore University Hospital – Northwell Health

Study Enrollment Procedures:

Institutional PI & Co-PI will determine a patient's eligibility based on SOC testing and procedures used in treating patients with aneurysms.

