10. STATISTICAL CONSIDERATIONS

Design:

The clinical trial will be conducted under a common umbrella protocol developed by the primary site (UTH) with the intention of combining data from all satellite centers for analysis. Each investigational site will give utmost importance to follow the study protocol to maintain consistency in study execution at all centers. Patients will be randomly assigned to 3 treatment groups in a 1:1:1 allocation ratio. The three therapeutic regimens to be considered are:

Group 1: nicardipine (Cardene) 5 mg per circulation in 25 mL of 5% Dextrose,

Group 2: verapamil 10 mg per circulation in 10 mL saline

Group 3: Cocktail agents: 5 mg in 25 mL 5% Dextrose + verapamil 10 mg in 10 mL saline + nitroglycerin 200 mcg in 4 cc of D5W per circulation.

A maximum of 330 subjects, 110 per treatment arm, will be randomized. The trial includes interim analyses that may reduce the maximal sample size if clear differences emerge among the arms during the conduct of the trial.

Interim Analyses:

Interim analyses will be performed to allow for discontinuing enrollment to treatment arms due to futility. After approximately 90 subjects have been randomized, 30 per arm, interim analyses will begin at the next quarterly Data and Safety Monitoring Board (DSMB) meeting. Subsequent interim analyses will be performed to coincide with DSMB meetings, which will occur after 40 subjects, 70 subjects, 110 subjects, 165 subjects, and 248 subjects have completed the study, and at the conclusion of the study (330 subjects).

At each interim analysis, an Analysis of Variance (ANOVA) will be performed to compare the PIIR results across treatment arms. If the overall treatment effect is significant with a p-value<0.05, then pairwise treatment comparisons will be performed. If any pairwise comparison is significant at a Tukey's adjusted two-sided p-value of 0.02 (p< 0.02), the poor performing arm will be dropped from the randomization scheme. If multiple arms are dropped and only one treatment arm remains open for randomization, that arm will be declared as best, and the clinical trial will end. Pairwise comparisons will only be performed if the overall treatment effect in the ANOVA is significant.

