A maximum of 110 subjects will be randomized to each treatment arm, for a total sample size of 330. If an arm or arms are dropped early, the final sample size will be less than 330. For example, suppose an interim analysis is performed after 70 subjects are randomized to the 3 treatment arms (total sample size 210). Suppose further, at the interim analysis one arm is dropped, and the remaining two arms continue to enroll to completion. The final sample size will be 290, i.e., 70 subjects in the dropped treatment arm, and 110 in each of the remaining treatment arms.

Enrollment will continue while the interim analyses are performed

Final Analyses:

All patients will be included in analyses utilizing the Intent-to-Treat approach that includes all subjects randomized in their randomized treatment arm regardless of treatment received.

At the final analysis, the primary outcome measure, PIIR will be compared between treatment arms using an ANOVA model. All data will be used in the final analysis, including any arms that may have been dropped from the randomization. If the overall treatment effect in the ANOVA model is significant at the two-sided, 5% level, then pairwise comparisons among treatment arms will be conducted using Tukey's adjusted p-values with p<0.0330 declared as statistically significant. This value controls global type I error (mistakenly claiming any pairwise difference when all treatments are equal) accounting for 6 interim analyses at the anticipated accrual rate of 2 years. If accrual significantly deviates from the anticipated accrual rate, further trial simulations will be conducted to determine an appropriate adjustment for the actual number of interim analyses conducted.

Descriptive statistics, means, medians, and standard deviations, will be reported for PIIR in each treatment arm. The two-sided 95% confidence interval will also be presented for the PIIR in each treatment arm.

The key secondary outcome, mRS (Modified Rankin Scale) at 3-months post-treatment, will be summarized by treatment arm by reporting the counts and proportions in each mRS category. Comparisons among treatment groups will be made using a Chi-square test.

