Additional secondary outcomes include SAE (severe adverse event) occurrences and the rate of treatment failure with balloon angioplasty. These outcomes will be summarized descriptively by presenting rates and proportions. Exploratory analyses comparing outcomes between treatment arms will be made using a Chi-square test.

Additional exploratory multivariable linear regression models will be created for the PIIR outcome, adjusting for treatment groups and additional baseline factors.

The analyses for the secondary outcomes are considered exploratory and no adjustments for the multiple tests and multiple comparisons will be made. Results will be interpreted cautiously understanding the some results may be significant at the 5% level due to chance alone.

Sample Size Justification:

Simulations were performed to estimate the power of the study for the primary outcome measure, PIIR, with a maximum sample size of 330 (110 per treatment arm) and the interim analyses for possible early arm dropping. A range of scenarios of PIIR were examined; the key scenarios used to power the trial are presented in Table 2.

Table 2.

Scenario	Treatment Arm 1: Nicardipine (N)	Treatment Arm 2: Verapamil (V)	Treatment Arm 3: Combination (C)
Combo 20	0.10	0.10	0.30
Mixed 1530	0.10	0.15	0.30

Note that the scenarios are both in favor of Verapamil over Nicardipine, but the results are symmetric if Nicardipine and Verapamil were reversed.

The trial will make every pairwise comparison:

- N versus V
- N versus C
- V versus C

The simulations focused on the V>N, C>N, and C>V comparisons. The following table presents the expected (mean) sample size and probability that the combination treatment regimen is better than the verapamil regimen, i.e., Pr(C>V), the main comparison of interest. Power is defined as the probability of identifying the superiority of the best dose over the other two doses.

Table 3.

Scenario	Expected N	Power Pr(C>V)
Combo 20	177	0.95
Mixed 1530	211	0.77

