Table 3 demonstrates, that for a hypothesized scenario of "Combo 20" where the combination therapy PIIR is 0.30 compared to 0.10 in Nicardipine and Verapamil, the study will have over 90% power and an expected sample size of 177. Both the Nicardipine and Verapamil arms would have been dropped at interim analyses before they reached their maximum enrollment of 110. If the scenario of "Mixed 1530" is observed, a situation where the Nicardipine arm PIIR is 0.10, the Verapamil arm PIIR is 0.15 and the combination arm is 0.30, the study will have 77% power and an expected sample size of 211. Again, both the Nicardipine and Verapamil arms would have been dropped at interim analyses before they reached their maximum enrollment of 110.

Missing Data and Dropout Rate: We do not anticipate missing data for the primary outcome PIIR as the angiogram will be performed 10 minutes post-infusion. For the secondary outcome, mRS at 3-months, based on previous studies, we estimate up to a 20% loss follow-up. Efforts will be made to keep all patients in the study through the 3-month follow-up visit. Substantial efforts will be made to ensure complete follow-up. Rates of missing data and loss to follow-up will be reported by treatment arm. We will attempt to document maximum amount of information regarding the status of these

patients who drop out. This procedure will help to compare characteristics of those patients who completed the study with those who did not.

Data and Safety Monitoring:

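### Up to 20% of 3-month mRS scores are expected to be missing, and the plan gives no method for them beyond a chi-square test that by default uses only followed patients

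*Combined protocol and SAP*

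**What the plan says.** All of this is in the combined protocol and SAP.

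- **Analysis population (Section 10, Final Analyses).** "All patients will be included in analyses utilizing the Intent-to-Treat approach that includes all subjects randomized". The rest of the sentence keeps each subject in the allocated group, whatever was actually given.
- **mRS analysis (same subsection).** The 3-month mRS is tabulated for each arm as numbers and percentages per category. The comparison is one sentence: "Comparisons among treatment groups will be made using a Chi-square test". No mRS analysis set is stated.
- **Expected loss (Section 10, Missing Data and Dropout Rate).** No missing data are expected for PIIR. For the 3-month mRS, "we estimate up to a 20% loss follow-up". The plan is to work at complete follow-up, report missingness by arm, document the status of patients who drop out, and compare them with completers.
- **Follow-up (Sections 6 and 7).** If the clinic visit is missed, the investigators contact the patient by phone or email, with mRS and NIHSS as the minimum data. Patients whose intervention was discontinued are still followed.
- **Data already collected (Section 4).** "Modified Rankin Scale, NIHSS (before treatment, at discharge, and at 3 months after discharge".
- **Status (Section 10).** "The analyses for the secondary outcomes are considered exploratory and no adjustments for the multiple tests and multiple comparisons will be made".

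The documents contain no imputation, model-based method or sensitivity analysis for a missing mRS.

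**The concern.** A chi-square test on mRS categories needs a category for every patient. Without a rule for patients who have none, the analysis that will be run is the followed-only one. The arms are then compared in a subset chosen after randomisation.

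The mRS carries the trial's only stated secondary objective and is its main patient-level outcome. Treating physicians know the assigned arm, and the investigators make the calls when a visit is missed; nothing says that the caller is blinded. An arm can also be dropped early, so arms may enrol over different calendar periods. Each of these makes arm-specific loss possible, though none shows that it will occur. A method chosen once results are visible would be open to criticism, and the data for a better method are already being collected.

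**Working it through.** **Inputs from the documents.** "A maximum of 330 subjects, 110 per treatment arm, will be randomized". Loss is at most 20%. Expected N is 177 or 211 (Table 3). The documents do not derive the 20%, and they give no mRS distribution, effect or power, so there is no plan figure to reproduce.

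**Inputs that are assumptions.** A two-category mRS (good or poor outcome), true good-outcome rates of 30% to 65%, and all loss patterns below.

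**1. Number missing at the ceiling.**
- Per arm: 110 × 0.20 = 22, leaving 88.
- In total: 330 × 0.20 = 66, leaving 264.
- At expected N: 177 × 0.20 = 35.4 and 211 × 0.20 = 42.2.

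**2. What the data alone can exclude.** With observed rate o and 20% missing, an arm's full rate lies between 0.8·o and 0.8·o + 0.2. For o = 50%: 44/110 = 40% to (44 + 22)/110 = 60%. For an observed arm difference d, the full difference lies between 0.8·d − 0.2 and 0.8·d + 0.2:
- d = 0 is compatible with −20 to +20 points.
- d = +15 points is compatible with −8 to +32 points.

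These are extremes, not expectations.

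**3. Same outcome-dependent loss in every arm.** Let p be the true good-outcome rate, and g and b the proportions of good and poor outcomes lost. The observed rate is p(1 − g) / [p(1 − g) + (1 − p)(1 − b)]. Take g = 0.10 and b = 0.30.
- No true effect, p = 50%: 0.45/0.80 = 56.3% in every arm. The difference stays 0. In a simulated three-arm chi-square (88 per arm, 40,000 runs), with poor outcomes lost 3 times as often, 20% loss overall and p from 30% to 60%, rejection was 4.8% to 4.9%.
- True 50% v 65%: observed 56.25% v 0.585/0.830 = 70.5%. The risk difference is 14.2 instead of 15 points. The odds ratio is unchanged: (0.585/0.245)/(0.45/0.35) = 1.86 = (0.65/0.35)/(0.50/0.50).

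So there is little or no bias.

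**4. Outcome-dependent loss in one arm only.** Loss is 20% in every arm, with no true effect. In one arm poor outcomes are lost 3 times as often; elsewhere loss is random.
- p = 30%: g = 0.2/(0.3 + 3 × 0.7) = 0.083, observed 0.30 × 0.917/0.80 = 34.4%, a false difference of 4.4 points.
- p = 60%: g = 0.2/(0.6 + 3 × 0.4) = 0.111, observed 0.60 × 0.889/0.80 = 66.7%, a false difference of 6.7 points.
- Simulated rejection is 9% to 14% against a nominal 5%.

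**5. Loss rate differing by arm.** True rate 50% in both arms, total loss L of 10% in one and 30% in the other, poor outcomes k times as likely to be lost. Then g = L/((1 + k)/2), and the observed rate is 0.5(1 − g)/(1 − L).
- k = 2: 0.5 × 0.933/0.90 = 51.9% v 0.5 × 0.80/0.70 = 57.1%, a false difference of 5.3 points.
- k = 3: 0.5 × 0.95/0.90 = 52.8% v 0.5 × 0.85/0.70 = 60.7%, a false difference of 7.9 points.

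**6. Extreme pattern.** If one arm loses mainly good outcomes and the others mainly poor ones (3 to 1, 20% loss overall), the false difference is 11 to 12.5 points and rejection is 37% to 39%. This is a limit, not a forecast.

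**The case against.** The strongest objections, and what stands of each:

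- **The plan does not contradict itself.** A reader might infer that a followed-only chi-square breaks an explicit intent-to-treat promise. The documents do not support that. The sentence ends with analysis in the assigned arm whatever treatment was received, so it deals with allocation and adherence and is silent on missing outcomes. The followed-only analysis set is itself inferred from silence. This objection stands: the two statements are unreconciled, not opposed.
- **Outcome-dependent loss does not by itself bias the comparison.** A reader might infer that it does because disabled patients may be harder to follow. Step 3 shows otherwise, so this stands too. The documents do not show that loss will differ by arm.
- **The plan has mitigations.** Phone or email contact and the retention efforts may reduce loss, and reports by arm may expose an imbalance. That stands, but no analysis step follows if an imbalance appears.
- **The sizes are assumed.** The 20% is a ceiling, and the 30% loss in step 5 exceeds it for that arm, although the two-arm average is 20%. Step 4 stays within the ceiling in every arm and still gives 4.4 to 6.7 points.
- **The outcome is exploratory and unpowered.** This stands and limits the severity.
- **Imputation is one choice among several, and may be unstable in a small dropped arm.** This is fair, and the fix allows for it.

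**Conclusion.** The gap is real and of limited weight. At the stated ceiling, up to one mRS in five has no planned treatment in the analysis, and the default comparison omits those patients. The firm parts are the count missing and the absence of any method. The bias of about 4 to 8 points is conditional: it needs a loss rate or mechanism that differs by arm, under patterns assumed here. If the mechanism is the same in all arms, the null difference and the odds ratio are preserved.

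The plan is not shown to be wrong as written, and the PIIR conclusion does not depend on this. The case for change is that discharge mRS and NIHSS are already collected. Using them recovers information and removes bias that discharge status explains. This is a cheap improvement.

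**What to change.** In Section 10, next to the mRS analysis:

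1. State that the mRS analysis includes all randomised patients in their assigned arm, with deaths scored as 6. Say so explicitly, because the adverse-event definitions in Appendix III leave some deaths out for endpoint purposes.
2. Multiply impute a missing 3-month mRS from discharge mRS and NIHSS, pre-treatment mRS and NIHSS, age and centre. Impute separately by arm, or with arm as a term in the model if an arm is dropped early and is small.
3. Name a test that can be pooled across imputations, for example a Wald test of the arm terms in an ordinal logistic model combined by Rubin's rules.
4. Report two sensitivity analyses: the followed-only chi-square, and a tipping-point analysis that lets non-random loss differ by arm.

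The cost is SAP wording and a little more analysis, with no new data. The downside is dependence on the imputation model, which the sensitivity analyses make visible. Imputation from observed data cannot remove bias from loss that discharge status and the other predictors do not explain; the tipping-point analysis is there for that.

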APPENDIX

- I. List of Participating Centers:
- 1. The University of Texas Medical School at Houston
- 2. University of Illinois in Chicago
- 3. Geisinger Health System
- 4. North Shore University Hospital Northwell Health
- 5. Memorial Hermann Hospital- At The Woodlands

II. Drug Information: The dose of the each medication set in this study is based on the limited clinical data available for each agent.

1) Nicardipine: a dihydrophyridine calcium channel blocker, the therapeutic effect is believed to be related to the selective inhibition of transmembrane calcium ion influx into vascular smooth muscle, resulting in a reduction of free calcium ions in these cells and disruption of actin-myosin interaction essential to muscle contraction ⁹. The dose used frequently in IA therapy is ranges 2 - 25 mg/each arterial territory, mean dose 5.7 +/- 4.3 mg ⁶. High dose IA nicardipine results hypotension, in some cases, even dose ranging from 4 to 7.5mg.

2) Verapamil: a phenylalkylamin calcium channel blocker that inhibits voltage-gated calcium channels in the arterial wall smooth muscle cells and results in vasodilation. It has been observed that there were no significant changes in BP, HR or ICP after administration of more than 20mg of IA verapamil ⁵.

3) Nitroglycerin: has been used in cerebral vasospasm treatment for a couple of decades. It has been reported dose of single vascular territory used up to 700 mcg without major hemodynamic instability.

III. Adverse events:

Term	Definition
Adverse Event (AE)	Any untoward medical occurrence, unintended disease or injury, or untoward clinical signs (including abnormal laboratory findings) in subjects, users or other persons, whether or not related to the investigational drugs.
	NOTE 1 This definition includes events related to the investigational drugs. NOTE 2 This definition includes events related to the procedures involved.
Adverse drug effect	Any AE related to the use of an investigational drug.
Serious adverse event	 Any AE that a) led to death, b) led to serious deterioration in the health of the subject that either resulted in 1) a life-threatening illness or injury, or 2) a permanent impairment of a body structure or a body function, or 3) in-patient or prolonged hospitalization, or 4) medical or surgical intervention to prevent life-threatening illness or injury or permanent impairment to a body structure or a body function, NOTE: Planned hospitalization for a pre-existing condition, or a procedure required by this Protocol, without serious deterioration in health, is not considered a serious adverse event. (ISO 14155, 2011)
Technical Event	A study procedure related event.
Stroke	New Stroke event, worsening of motor, sensory or speech function. Cant be explained by cerebral vasospasm and or pre-existing aSAH Clinically and radiographically.
Neurologic Death	For the purposes of study endpoints, neurologic death is defined as any death determined to be of neurologic cause. This definition excludes: death due to rupture of a nonindex aneurysm or as a consequence of treatment of a nonindex aneurysm.
Death	For the purposes of study endpoints, death excludes death of accidental causes or death due to rupture of a nonindex aneurysm or as a consequence of treatment of a nonindex aneurysm.

Study procedure related Minor complications might include:

Nausea and/or vomiting (post-anesthesia) Mild headache Groin discomfort: mild pain and or bruising at the incision site

Study Procedure related **Significant complications** (catheter induced: different from preexisting cerebral vasospasm & SAH induced ischemia): Intra-cranial catheter induced spasm of the treated segment of artery or branches Stroke (ischemic, hemorrhagic, TIA) Hemiplegia Aphasia Visual impairment or blindness Intra cranial artery tear (hemorrhage) Femoral artery occlusion due to catheter

Study Procedure related Very Rare side effects may include: Death Renal failure due to dye induced Seizure Infection Blood vessel or nerve damage Decreased blood flow in the leg on the side of the groin puncture A pseudoaneurysm may develop as a result of injury to all the layers of a vessel wall resulting in a hematoma Air embolism Mental status changes Total occlusion of the treated blood vessel segment or other blood vessels.

DRUG RELATED adverse events & overdose effects:

NOTE: All drug related adverse events & overdose effects listed below are excerpts from the package inserts. The package inserts used as a reference are for IV doses since no data is available on Intra-arterial package inserts

